In the primary DISCOMS trial, we employed a five person Data Safety Monitoring Board composed of a patient, a statistician and three neurologists to assess safety within the study every 6 months and generate a formal report concluding it was appropriate, or not, to continue the study. As of 9/14/2020, they have concluded in each report there were no reasons to discontinue the study. As there have been no significant safety issues, and many of the potential enrollees in the extension trial will have already finished their participation, we will simplify things in the extension trial here. A Medical Monitor will be employed to perform twice yearly reviews of the safety data and certify that it is acceptable for the study to continue. It is possible that, in spite of a prolonged period with no new inflammatory disease activity, those who discontinue their DMTs will have a substantial increase in inflammatory disease activity, or progressive disease based on EDSS, or worsened patient quality of life, compared to continuers. This could be especially important for those discontinuing natalizumab, where there remains significant concern, and also disagreement, about the potential for not just recurrence of disease activity, but also significant rebound (i.e., higher than prior baseline) of disease activity.

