Blinding of outcome measures is very important. As this is a pragmatic study in which the research component is added on to the basic clinical visit, the Treating Physician/PI will have obtained a relapse history as part of that routine visit, yet is not blinded to the patient's medication assignment. The definition of relapse includes performance of the EDSS, and the separate EDSS Examining Clinician will be blinded to medication assignment, as well as to the relapse history, when doing the EDSS. While it might be preferential to have a relapse assessor separate from both the PI and the EDSS rater, this is impractical due to costs, the requirement to have a third clinician available at the visit, and the extra time of the visit. Thus, we will ask the PI to do a relapse assessment based on symptoms, but only make this information available to the EDSS Examining Clinician AFTER the EDSS is completed. The EDSS Examining Clinician will make the final assessment as to whether a Protocol defined relapse has occurred. While MRI readers and Examining Clinicians will be blinded to the patient's medication assignment, patients will not be blinded to medication assignment. Thus interpretation of the secondary Aims and Hypotheses as they relate to PROs will be potentially confounded by patient bias.

It is possible a patient may have asymptomatic changes on a surveillance spine MRI scan, which is not part of the protocol or SOC. Most new spine lesions will have clinical symptoms and signs associated with them, however, limiting the significance of this issue.

This protocol, if taken as an independent study of participants who have been randomized and followed on treatment or off treatment for two years for an additional follow-up period will not have sufficient power to answer the question of non-inferiority during this extension period. If taken as a continuation of the original protocol, it then operates under the power considerations designed in the original protocol (NCT03073603). We acknowledge the insufficient power of this extension study to address non-inferiority, but still expect to obtain valuable information. Through this extension, we will be able to track rates of relapse or MRI scan changes and collect information on effects of withdrawal from therapy, disease progression, and quality of life of these older MS participants over a longer follow-up period.

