F.Data Analysis Plan: All DMTs will be treated as a single group, as the analysis is not powered to ensure an effective subgroup analysis by DMT type. With an assumption of 100 finishing participants, this will allow an attempt at subgroup analysis by sex, age epochs, disease duration, and others. Patients with all forms of MS, RRMS, SPMS and PPMS who participated in the original DISCOMS trial will be offered participation, and because patients with all forms of progressive disease tend to act in a similar manner with regard to ongoing disease activity, SPMS and PPMS will be merged into a single category, progressive patients, for any sub-analysis.

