a. Aim #1: Proposed Data Analysis: We will perform an extension of the primary DISCOMS study, that being the time to failure defined as a protocol-defined disease event with each treatment group extending the understanding of the durability of the assigned treatment arm beyond the original DISCOMS follow-up period. A countable event will be a new protocol-defined relapse, and/or a new brain MRI lesion. We will estimate the long-term differences between the two treatment arms. Further by linking the time to event within the 100 participants with the original DISCOMS event free survival estimates, we can further evaluate the null hypothesis of inferiority with the proportion of disease events for the discontinue group being 0.08 proportion worse (our original noninferiority margin) at later time points of follow-up than the proportion for the continue group under the alternative that the two rates are equal. Because of the expected small numbers of events, we will use Kaplan-Meier estimates of the differences to obtain a confidence interval for comparing the proportions with individuals counted at their respective event times or censored based on their last known status. If the upper bound of the 95% confidence interval for the difference between the groups is less than 0.08, then we can reject inferiority and rule out discontinuation increasing the disease event proportion by 0.08 or greater. Our primary goal here is to estimate these differences given the relatively small sample size included, but we will calculate these values using the data obtained. In the unlikely event the proportions are relatively large, we will also calculate estimates and confidence intervals for relative risks. Larger numbers of events would permit the fitting of more complex models, but to date we know that the majority have not failed although their assignments are not known to us.

b. Aim #2: Proposed Data Analysis: We will calculate estimates and confidence intervals, using exact methods as necessary, for the proportion of disease events in both the discontinue and continue groups after this extension

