study. Aim #2 will be mostly descriptive and assesses progression of disability as noted on the EDSS, and this will be defined as an increase of at least one point, confirmed at 6 months, for those with a baseline EDSS \leq 5.5, or a change of at least 0.5 for those with EDSS of 6.0 or greater at baseline. The estimates of the population from the origin of the study will be model based since participants in the extension study must by criteria have not had progression over the initial period of follow-up. Nevertheless, we will have the proportion at the end of the formal DISCOMS study and can apply the successive failure rates using conditional probability to obtain an overall estimate of the progression rate after 2 or 3 years and further can compare the post DISCOMS experience between the two arms given the participants were free of events at entry into the Extension study. Outcomes assessed will include % of patients with progression in each group as compared to the final EDSS in DISCOMS, and mean change in EDSS in each group overall (via the extension period. The latter analyses will help identify if the rate is increasing over time or if the rate is relatively stable over time.

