Sample Size: The sample size was driven by budget considerations and the expected number who could complete the extension within a reasonable time period. We chose to focus on those who have been maintained in their assigned treatment arms from the original randomization to allow extension of time to event analyses. We considered including those who would go back on therapy or who subsequently stopped therapy, but felt that not only would the numbers likely be smaller than desired, they would diminish the available slots for the most informative participants (those maintaining their randomized assignment). Thus, while we expect roughly equal numbers from both treatment arms (the alternative hypothesis originally posed, that the two treatments are equal), we will have approximately 50 participants per arm. If we assume that there are 50 participants in each arm and 20% of the discontinue arm fails compared to 6% (10 and 3 of each group respectively), a fisher's exact test would yield a one sided p-value of 0.036, sufficient to say the discontinue group has done worse. We also plan to test for baseline differences between the two groups, using data from the original RCT, and will adjust for any significant baseline differences.

It may be that there are differences between those with relapsing forms vs progressive forms of MS after discontinuation of their DMT. While we will not be powered to assess differences separately by relapsing or progressive forms, we have a pre-planned descriptive analyses for this important question, as well as other subgroup analyses. These will include analysis based on sex, age, disease duration, time since last relapse, specific DMT, and others since study outcomes will not be powered for stratification by MS type or heterogeneity of treatment effects, they will be simply examined as estimates of longer term treatment follow-up.

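### The non-randomized extension comparison is adjusted only for baseline differences that test significant, which on average leaves about 60% to 30% of a covariate's bias at true imbalances of 0.2 to 0.4 SD

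*Combined protocol and SAP*

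**What the plan says.** The rule stands in section III.F, in the Sample Size paragraph. The protocol states: "We also plan to test for baseline differences between the two groups, using data from the original RCT", and it "will adjust for any significant baseline differences". It gives no significance level, covariate list or model, and does not say which aims are covered.

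The surrounding text bears on this in five ways:

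- **Design.** Sections II and III.C describe the extension as non-randomized. Entry requires finishing DISCOMS without an event and keeping the assigned strategy. Table 1 shows 36 of 42 discontinuers and 25 of 42 continuers planning to keep theirs.
- **Aim 1 (III.F.a).** "Our primary goal here is to estimate these differences given the relatively small sample size included". The extension result also enters a longer-term estimate ("Further by linking the time to event within the 100 participants with the original DISCOMS event free survival estimates"), which is compared with the 0.08 margin.
- **Aim 2 (III.F.b).** The sponsor "can compare the post DISCOMS experience between the two arms given the participants were free of events at entry into the Extension study". No adjustment is described.
- **Power (III.E).** "We acknowledge the insufficient power of this extension study to address non-inferiority".
- **Other mentions of control.** Section III.A says that PDDS will be used to control for disability, but no analysis in III.F does so, and PDDS at the final visit is itself an Aim 3 outcome. Section III.D says of rebound activity: "This could be especially important for those discontinuing natalizumab". Section III.F says: "All DMTs will be treated as a single group". DMT class would therefore be adjusted for only if it tested significant.

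**The concern.** Participants who reach the extension have selected themselves, and at different rates by arm, so the original randomization no longer protects the comparison. In that setting a covariate should be adjusted for because it predicts outcome and may differ between arms. A p-value measures neither. With about 100 people, a non-significant baseline test mostly reflects low power.

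Under the stated rule, chance decides whether a given confounder is handled, and on average only part of its bias is removed. Since the plan puts estimation ahead of testing, bias in the estimate is what matters. It would also pass into the linked estimate that is set against 0.08.

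**Working it through.** **Figures in the plan.** 36/42 = 85.7%, 25/42 = 59.5% and 36/61 = 59.0%, matching the stated 86%, 60% and 59%. The Sample Size paragraph's example (10/50 versus 3/50, Fisher's exact, one-sided) gives p = 0.0357, matching 0.036. That example is an unadjusted comparison.

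**Step 1: what the rule does to one covariate.** Inputs: n = 59 and 41 (from the 59% projection), covariate SD = 1, true imbalance d (assumed), alpha two-sided (assumed). Let SE = √(1/59 + 1/41) = 0.2033, m = d/SE, and c the critical value. The observed difference D is removed only when it is significant, so the average share of bias left is

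E[D × 1(not significant)]/d = {m·P − [φ(c − m) − φ(−c − m)]}/m, where P = Φ(c − m) − Φ(−c − m).

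For d = 0.3 and alpha 0.05: m = 1.4755, P = 0.686, and the share is (1.4755 × 0.6857 − 0.3537)/1.4755 = 0.446. Replacing the normal test with a t-test on 98 df (simulation) gives slightly higher values:

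| True imbalance (SD) | Adjustment triggered, alpha 0.05 | Bias left, alpha 0.05 | Bias left, alpha 0.10 | Bias left, alpha 0.20 |
|---|---|---|---|---|
| 0.2 | 16% | 60% | 43–44% | 25% |
| 0.3 | 31% | 46% | 31% | 16% |
| 0.4 | 50% | 30–31% | 19% | 9% |

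With 50 per arm at alpha 0.05 the shares are 59%, 45% and 29%. Adjusting whatever the test result leaves about 0% in a linear model with the covariate measured without error. The percentages average over significant and non-significant tests and are approximate for Kaplan-Meier differences.

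**Step 2: which imbalances are plausible.** Suppose four independent covariates, balanced at randomization, each drive the decision to stay. Even if their sum decided staying completely, the mean of that standardized sum among stayers is φ(z)/p. This is 0.263 at p = 0.857 and 0.651 at p = 0.595. Dividing by √4 gives 0.132 and 0.326 per covariate. The ceiling is therefore 0.326 − 0.132 = 0.19 SD each if selection runs the same way in both arms, and 0.33 SD if only the continue arm selects. In the second case, reaching 0.3 SD needs an odds ratio near 8 per SD on every covariate. If the arms select in opposite directions, an odds ratio of about 2.1 per SD is enough.

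**Step 3: size on the risk-difference scale.** Simulation: 59:41, four normal covariates all pushing risk the same way, odds ratio 1.5 per SD, logit intercept −2.5, no true effect, rule at alpha 0.05, 6,000 runs. Overlap-weighted results are shown; with inverse-probability weights the bias under the rule differs by at most 0.03 points.

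| Imbalance on each (SD) | Discontinue arm | Unadjusted bias (points) | Under the rule | Fixed set |
|---|---|---|---|---|
| 0.10 | lower risk | −1.3 | −0.9 | −0.1 |
| 0.10 | higher risk | 1.3 | 0.9 | −0.1 |
| 0.15 | lower risk | −1.8 | −1.2 | −0.1 |
| 0.15 | higher risk | 2.3 | 1.5 | 0.0 |
| 0.20 | lower risk | −2.3 | −1.4 | 0.0 |
| 0.20 | higher risk | 3.0 | 1.8 | 0.1 |

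The standard deviation of the estimate is 5.6 to 6.4 points. With two covariates pointing each way, the bias is near zero under every approach.

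**Step 4: the linked estimate.** If both arms leave DISCOMS with event-free probability S, the linked difference is S × (extension difference) and carries S times the bias. For an assumed S of 0.80 to 0.95, a bias of 1 to 1.5 points becomes 0.80 × 1 = 0.8 to 0.95 × 1.5 = 1.4 points, or 10% to 18% of the 8-point margin.

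**The case against.** The strongest reply has four parts.

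- **The inputs are assumed.** Neither the imbalances nor alpha is in the documents, and at alpha 0.20 the share left falls to 25–9%. This stands, and is why the result is given as a range. It does not rescue the rule, because no alpha makes a p-value a measure of confounding.
- **The harm is small.** A bias of 1 to 1.5 points against a standard error near 6, with simulated interval half-widths of about 11 to 14 points, would rarely change a conclusion. III.E already concedes that the extension alone cannot settle non-inferiority. This stands and limits the severity.
- **A fixed set is not clearly better on total error.** With four covariates 0.3 SD apart, root mean squared error under inverse-probability weights is 5.8 for the rule against 5.6 for the fixed set, but 7.5 against 7.6 in the reverse direction. With mixed directions, leaving the estimate unadjusted is best. Overlap weights give 5.9 against 5.7, 7.0 against 6.7 and, mixed, 6.1 against 6.2. So the case for a fixed set rests on bias and transparency, and no one weighting scheme should be imposed.
- **The plan explains itself elsewhere.** III.F says that more events would allow more complex models, and it states and defends an assumption of similar risk across DMTs. Pooling DMTs is therefore a declared simplification, and the natalizumab remark in III.D does not contradict it. Likewise, Aim 3 separates baseline from extension entry, so baseline in the Sample Size paragraph most naturally means DISCOMS entry, although III.C makes Month 24 the extension baseline. These are secondary points.

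A reader might also infer biases of several points. Four covariates each 0.3 SD apart would give an unadjusted bias of 3.3 or 4.7 points in simulation. The documents do not support that as an estimate of likely harm: Step 2 shows that same-direction selection at the observed retention cannot produce it, and selection in the continue arm alone would have to be extreme. Opposite selection in the two arms, or selection through consent and event-free status, could add imbalance, but the documents do not quantify either.

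**Conclusion.** The concern holds as a weak stated rule, which is more than missing detail. In a comparison that the protocol itself calls non-randomized, adjustment depends on a test that would miss a 0.3 SD imbalance about 69% of the time at alpha 0.05, leaving on average about 46% of that covariate's bias. These shares rest on a 59:41 split, one continuous covariate and an assumed two-sided alpha.

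The absolute effect is probably modest: roughly 1 to 1.5 points at plausible imbalances, somewhat more at 0.2 SD if the discontinue arm is the higher-risk one, and near zero if confounders offset each other. A reader might conclude that the rule favours discontinuation or would reverse the finding against 0.08. Neither follows, since the direction is unknown and random error dominates. The sponsor should still change the rule, because the estimate affected is the stated primary goal and the change costs little.

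**What to change.** In the Sample Size paragraph of III.F, replace the significance rule with the following:

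- A short covariate set measured at DISCOMS entry, for example age, relapsing versus progressive MS, time since last relapse, and EDSS. Fix it before arm-level outcomes are examined and use it whatever the p-values. Aim 1 states that failures by assignment are not known to the team; if that still holds, the set can be fixed now.
- Other baseline variables described by standardized differences, without tests.
- The adjusted between-arm difference with its 95% CI, reported beside the planned unadjusted one.

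For Aim 1, with few events, a single propensity score for arm with overlap weights is a suitable option, because it models the arm split and not the events. The choice of method is the sponsor's, but it should be named in advance.

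**Cost.** SAP wording and modest programming, with no new visits. Age, MS type and time since last relapse are already planned subgroup variables; availability of EDSS at DISCOMS entry should be confirmed. Some precision may be lost: about 0 to 0.2 points of standard deviation with overlap weights, and up to about 1 point with inverse-probability weights (6.5 to 7.6 in the worst scenario run). There is no gain in total error if confounders point in different directions. The benefit also depends on choosing the right covariates, and unmeasured selection remains.
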